Colorectal cancer is a frequent type of cancer accounting for 600,000 deaths annually. Surgical resection remains the best treatment for long-term survival. However, studies suggest that events in the perioperative period can induce metastasis formation and tumor growth^{1,2,3}. Tumor cells are released into the blood stream during surgery and the surgical stress may create a favorable environment for dissemination of tumor cells into distant tissue^{4,5,6,7,8}. This is done by a cascade of pro-cancerous catecholamines, prostaglandins and cytokines combined with an impaired anti-cancerous cell mediated immune response^{9,10,11}.

Until recently, focus on the anesthetic management of cancer patients has been limited. Relatively small alterations in the perioperative anesthetic management may play a tremendous role in tumor progression⁹. Optimizing anesthesia to reduce the surgical stress response could improve recurrence rates and long-term outcomes for cancer patients by inhibiting perioperative metastasis formation. Regional anesthesia and amide local anesthetics are suspected to calm the immunologic storm of prostaglandins, catecholamines and cytokines when used in the perioperative phase^{12,13,14,15,16,17}. Furthermore, volatile inhalational anesthesia is thought to modulate the immune system in a pro-cancerous way, while propofol may have opposite effects^{18,19,20,21,22}. Many of these recent studies are statistically underpowered and susceptible to bias, and experts in cancer treatment and anesthesia have emphasized the need for further research within this specific field^{5,23,24}.

In this study we aim to characterize differences in the immunologic response to surgery between inhalational, total intravenous and epidural anesthesia. This will be done by analyzing blood samples obtained in the perioperative period in patients undergoing different modes of anesthesia. We will furthermore describe the quality of recovery for patients anesthetized with the different methods

Objectives

We hypothesize that the immunologic response to surgery and metastasis progression are influenced by the anesthetic technique.

Methods

The study is initiated by Center for Surgical Science, Department of Surgery, Zealand University Hospital. It will be included in the Ph.D. studies of [name] at University of Copenhagen.

Design and approvals

This study, initiated by Center for Surgical Science, Zealand University Hospital, will be a prospective cohort study. Approval from Danish Data Protection Agency and the Regional Committee for Health Research and Ethics is required. The study will require informed consent from participants.

Permission to transfer data from the IMOX study will be obtained from the Danish Data Protection Agency. The trial protocol will be submitted to clinicaltrials.org before initiation of the trial. Manuscripts will be prepared according to the STROBE statement²⁵.

Study setting

The study will take place at Hvidovre Hospital. This is a Danish university hospital. It supports 500,000 people and is one of four main emergency hospitals in Copenhagen Denmark. About 300 laparoscopic colon resections are performed at this facility every year.

Intervention

Participants will undergo laparoscopic colon resection for cancer. They will be anaesthetized according to the standard operating procedure at Hvidovre Hospital (see appendix 1) with the exception that no dexamethasone is administered as it could modulate the immune response. This includes anesthesia induction and maintenance with intravenous propofol and remifentanyl. Patients will receive 4 mg ondansetron at the end of anesthesia.

A thoracic epidural catheter will be installed preoperatively and kept for up to three days. After an initial bolus with bupivacaine, continuous infusion of bupivacaine and sufentanyl will be used to maintain the epidural analgesic effect. Postoperatively the epidural will be paused or discontinued if it is displaced or if side effects occur. It will only be re-installed if there is still need of neuraxial analgesia.

Patients will follow a standard Enhanced Recovery After Surgery (ERAS) protocol used at the facility.

Blood samples will be obtained before surgery and at four time points postoperatively and patient files will be assessed for adverse events within 30 days from surgery.

Withdrawal criteria:

Patients can be withdrawn from the study for any of the following reasons:

- Failure to adhere to the anesthesia intervention described above- including failure to install effective continuous epidural anesthesia.
- Adverse events after surgery
 - Any complication over grade 2 in Clavien-Dindo²⁶ classification
 - Blood transfusion
 - Deep vein thrombosis or pulmonary embolism
 - Anastomotic leak
 - Acute renal failure
 - Infection (wound infection or systemic infection) during the observation period.
- After consultation patients can be withdrawn due to withdrawal of informed consent to participate in the study at the patients' own request at any time for any reason.

Population

Study group: The "Hvidovre population":

We will include patients undergoing laparoscopic hemicolectomy for cancer scheduled for anesthesia with total intravenous anesthesia combined with epidural anesthesia on Hvidovre Hospital according to the intervention described above.

Eligibility criteria:

Inclusion criteria:

1. Patients over 18 years
2. Patients diagnosed with colorectal cancer (UICC stadium I-III) and scheduled for laparoscopic hemicolectomy.
3. ASA class I-III (Classification of the American Society of Anesthesiology)

4. Patients scheduled for anesthesia with propofol, remifentanil and epidural anesthesia.
5. Signed informed consent

Exclusion criteria:

1. Known immune-defects
2. Patients undergoing neoadjuvant chemo or radiotherapy
3. History of previous cancer
4. Patients in immunomodulatory treatment within last 6 months
5. Daily oral or intravenous steroid-use
6. Patients that have undergone major surgery within one month before planned colon resection.

Control group: The “Zealand University Hospital population”

The immunological and oxidative stress in relation to abdominal surgery (IMOX) study is ongoing at Zealand University Hospital, Roskilde. It is a prospective explorative study cohort that consists of 60 patients undergoing laparoscopic colorectal cancer surgery. The aim of the study is to characterize the immunological and oxidative stress response to surgery. Outcomes similar to the primary and secondary outcomes of the ANIMOX-study are included in the IMOX-study. Patients are already included in the IMOX-study and blood samples are collected and kept in a bio bank.

We will retrieve data on our main outcomes from the IMOX study in our analysis. Only electronic data will be used and no biologic material will be transferred from the IMOX project to ANIMOX. The population will be stratified according to anesthetic technique, which, according to the standard operating procedure, is either total intravenous anesthesia with propofol and remifentanil or volatile anesthesia with sevoflurane combined with a fast acting opioid (remifentanil or sufentanil). Patients anaesthetized with other techniques including epidural or other regional blocks will be excluded from the analysis.

Biological samples

To characterize the immunological response to surgery we obtain blood samples for analysis on postoperative day -1, 1, 2, 3 and 10 (or at the visit on day 10-14 where pathology results are given).

Handling of blood samples

Blood samples will be drawn by a trained professional and analyzed immediately at the standard lab facilities at Hvidovre Hospital and destroyed immediately hereafter. The results will be accessible in Sundhedsplatformen.

Primary outcome:

The primary outcome will be changes in neutrophil to lymphocyte ratio from day 0 to day 1. Neutrophil to lymphocyte ratio has been linked to poor outcome after colorectal cancer surgery. The ratio will be estimated using absolute numbers from differential counts pre and postoperatively.

Blood samples

Standard blood samples will be obtained and analyzed immediately at each time point. These include Hgb, Leucocytes including a differential count, thrombocytes, ALAT, LDH, Alkaline phosphatase, bilirubin, INR, albumin, Na, K, Creatinine, CRP and Glucose.

Quality of Recovery – 15 questionnaire

At each time point (day -1, 1,2 and 10) the patients are asked to fill in the validated Quality of Recovery Questionnaire QoR-15²⁷. The QoR-15 questionnaire results in a score of 0–150. These outcome measures will be correlated with changes in immunologic outcome measures in the perioperative period.

Guidelines for oral and written consent and participant timeline

The first contact with a potential participant will be either during a stable phase of the primary admission, during an out-patient visit or during an introduction meeting prior to surgery. Patients will receive both oral and written information about the study. Patients will be contacted and a meeting where the inclusion will take place will be planned. An appropriately trained investigator will give information about the study including potential risks, harms and inconveniences. Before this meeting, patients will be informed that:

1. The patients have 24 hours or more to consider their informed consent.
2. An observer at the meeting can accompany the patient.

The meeting will take place in a quiet and undisturbed room. Amended to the patient information will be a document from the Central Ethical Committee with the title of "Your rights as a test subject in a biomedical research", which the patient will be recommended to read before inclusion.

Patients will have blood samples taken at four time-points - before surgery, day 1, day 2, day 3 and at the out-patient visit 10-14 days after surgery, where pathology results are given. The patient timeline is outlined in figure 1.

Participation is voluntary and no financial compensation will be given to participants.

Sample size

Study size

Due to the exploratory nature of this study, it is not possible to perform a valid sample size estimation. However, based on a pilot study of 45 patients undergoing laparoscopic hemicolectomy we found that the neutrophil to lymphocyte ratio increased 5.33 neutrophils/lymphocyte from preoperatively to postoperative day 1 (SD 3.33). With a power of 0.8 and an alpha value of 0.05 we will be able to detect a 50% smaller increase in neutrophil to lymphocyte ratio with 25 participants. As this power calculation is associated with much uncertainty we will include 30 evaluable patients (patients completing the study without meeting withdrawal criteria) to avoid a type 2 error.

We estimate that 10-20% of included patients will meet withdrawal criteria before completing the study. Therefore we expect that we need to include 36 patients to complete the study.

They will be compared to the patients included in the IMOX-study at Zealand University Hospital.

Recruitment timeline

Patients scheduled for laparoscopic hemicolectomy at Hvidovre Hospital will be screened for eligibility. 300 laparoscopic colon resections for cancer are performed at this facility each year and most of these are scheduled for total intravenous anesthesia with epidural anesthesia. With an inclusion rate of 50% we expect to be able to

include 30 participants that completes the study and does not meet the withdrawal criteria within 26-52 weeks.

We expect to begin inclusion in January 2019 and to finish the trial by 31st December 2019.

Data collection and management

To screen for eligibility to be included in the study we will request and obtain data on tumor stage, age, known immune defects, ASA-score, type of surgery, planned anaesthesia type and use of steroids.

After informed consent and inclusion in the study, data on demographics (comorbidities, age, sex), disease stage (clinical and pathological tumor histology), perioperative management (anesthesia type, medication, surgical procedure) and adverse events up to 30 days postoperatively will be obtained from the patient file. Nurses at the Surgical Ward will be trained to encourage participants to fill in the QoR-15 questionnaires. The questionnaires will be kept with the patient in a folder that will be returned at the time of discharge. The patient will bring one QoR-15 questionnaire home to fill in at day 10. This questionnaire will be returned at the pathology result visit at day 10-14.

Blood samples will be taken and handled by a trained health care professional and brought to the laboratory for preparation and analysis within one hour.

Patients who are discharged before blood samples are taken on day 1,2, and 3 will be asked if they wish attend the blood sampling as out-patients at the same timepoints. Patients who does not show up to, or does not have the final blood samples taken at the time of out-patient pathology results will be contacted and encouraged to have the final blood samples taken and return the last QoR-15 questionnaire.

Study data will be stored according to guidelines from the Danish Data Protection Agency and “databeskyttelsesforordningen” and “databeskyttelsesloven” will be adhered to.

Statistical analysis plan

Data will be analyzed using R, SAS institute or SPSS. All tests will be two-sided with $p < 0.05$ considered to be significant.

Data analysis

Data from the Hvidovre population and the Zealand University Hospital population will be combined to evaluate the effects of inhalational anesthesia (sevoflurane and opioid), total intravenous anesthesia (propofol and remifentanyl) and total intravenous anesthesia (propofol and remifentanyl) combined with epidural anesthesia (bupivacaine with opioid). Only electronic data will be used from the IMOX project – no biologic material will be transferred.

Baseline and clinical characteristics for patients, stratified for anesthesia type will be presented as frequencies for nominal, dichotomous and ordinal variables and medians with IQR for continuous variables. Outcome variables will be presented and described with appropriate tests. Depending on whether data is normally distributed or not, differences between the groups will be assessed using parametric or non-parametric statistics, respectively.

Risks, harms and inconveniences

Patients will receive the standard care at the respective hospital. The study does not influence any treatment or intervention related to the hospitalization.

Peripheral blood samples

Blood will be drawn from puncture of the cubic vein. The needle can cause minor discomfort including hematoma, which will disappear within few days.

QoR-15 questionnaires

Filling in the QoR-15 questionnaire will require a short amount of time and effort at the four time points.

Ethical considerations

Research within this field is until now very limited, but optimization of the anesthetic technique used for cancer surgery can benefit millions of people undergoing surgery for cancer in the future.

Approval from the regional scientific ethical committee is mandatory. Important modifications in the protocol will be communicated to the committee and approved before implementation.

Written consent from all participants will be obtained before inclusion as described above. Participants can at any time withdraw their consent.

All personal information about enrolled patients will be collected and protected according to Danish Law to ensure confidentiality before, during and after the study.

Data will only be assessed by participants of the study group according to the approval from the Danish Data Protection Agency.

Risk of random findings

We do not expect random findings that will affect participants, as the scope of this study is to explore mechanisms of the immune system in the short perioperative period. We will not perform genome or DNA analysis, which potentially could reveal unknown underlying genetic disease.

Publication of results

Results of the study will, regardless of the results, be submitted for publication in an international peer-reviewed medical journal. No personal data that can be directly linked to a participant will be published.

Economy

Budget

	DKK
Sample collection incl. test tubes	66,000
Presentation of results (travel and conference fees)	30,000
Publication fee	10,000
6 months salary for Ph.D. student [name]	275,000
Total	381,000

Funding

The study is initiated and will be funded by Center for Surgical Science, Zealand University Hospital. On an ongoing basis we will apply for grants from private or public foundations. We have received a grant from Hesse's Mindefond of 66,000

DKK for lab assistance for this project. Financial transactions and bookkeeping will be administered by Department of Surgery, Zealand University Hospital. Sources of economical support will be declared in manuscripts.

Insurance

Patients included in this study are covered by the insurance of Hvidovre Hospital. The project is included in “Patienterstatningsordningen”.

Conflicts of interest

None of the investigators have any conflicts of interest in this study.

References

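### Dexamethasone is withheld in the epidural group as a possible immune modulator, but the plan neither states nor handles its use in the IMOX controls, so both epidural contrasts may mix epidural with steroid exposure

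*Combined protocol and SAP*

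**What the plan says.** - **Epidural group.** The Intervention section applies the Hvidovre standard procedure "with the exception that no dexamethasone is administered as it could modulate the immune response". Appendix 1 lists dexamethasone at induction, so this is a deliberate departure made to protect the immune outcome.
- **Controls.** The Control group section states "We will retrieve data on our main outcomes from the IMOX study in our analysis". Patients are stratified by technique, which "according to the standard operating procedure, is either total intravenous anesthesia with propofol and remifentanil or volatile anesthesia with sevoflurane" with a fast-acting opioid. The only exclusion is again by technique: "Patients anaesthetized with other techniques including epidural or other regional blocks will be excluded from the analysis". Steroid is not mentioned.
- **Steroid criterion.** "Daily oral or intravenous steroid-use" is an exclusion listed under the Hvidovre group. It concerns daily use, not a perioperative dose.
- **Data items.** Data collection and management includes medication under perioperative management, taken from the patient file after consent and inclusion. On its face that means Hvidovre participants. It names neither dexamethasone nor IMOX.
- **Analysis.** Under Sample size, the Hvidovre patients are the study group: "They will be compared to the patients included in the IMOX-study at Zealand University Hospital". Under Data analysis, "Baseline and clinical characteristics for patients, stratified for anesthesia type will be presented", and "differences between the groups will be assessed using parametric or non-parametric statistics, respectively". No covariate, restriction or sensitivity analysis is given.

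**The concern.** The plan names a possible modulator of its own primary outcome and controls it on one side of the comparison only. All epidural patients come from Hvidovre. All patients with intravenous anesthesia alone or sevoflurane come from IMOX. Any dexamethasone use in IMOX would therefore enter both epidural contrasts and be read as part of an epidural effect, or would hide one. IMOX patients are already being included, so their exposure cannot now be standardised by design. What can still be done is to document it and set an analysis rule in advance.

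The sevoflurane versus intravenous contrast lies wholly within IMOX and is not affected by what was withheld at Hvidovre.

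**Working it through.** **Inputs from the documents (Sample size and Control group sections).** Pilot mean increase in NLR 5.33, SD 3.33; target a 50% smaller increase; power 0.8, alpha 0.05; 30 evaluable epidural patients; 60 IMOX patients, split by technique not given. Tests are two-sided (Statistical analysis plan).

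**The plan's own figure.** Target difference = 5.33 × 0.5 = 2.665. Normal approximation: n per group = 2 × (1.960 + 0.842)² × 3.33² / 2.665² = 24.5, so 25. The stated 25 reproduces if read as per group. This point does not change it.

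**Assumed inputs.** The documents give no dexamethasone effect, no share exposed and no control split. The illustration assumes a 1-unit effect on day-1 NLR change, a share f of controls exposed, and 30 controls in a contrast.

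**Bias.** Bias = f × effect, and zero if no control was exposed. SE = 3.33 × √(1/30 + 1/30) = 0.860. Results from the noncentral t distribution, two-sided 0.05, 58 df:

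| Share exposed | Bias | False-positive rate, no epidural effect | Power for 2.665 if the bias masks it |
|---|---|---|---|
| 0% | 0 | 5.0% | 0.862 |
| 10% | 0.10 | 5.2% | 0.835 |
| 25% | 0.25 | 5.9% | 0.789 |
| 50% | 0.50 | 8.8% | 0.697 |
| 100% | 1.00 | 20.8% | 0.478 |

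With 20 or 40 controls, the 50% row gives 8.0% or 9.4%, and the 100% row 17.5% or 23.2%. The assumed effect matters more than the split: at 2 units with all 30 controls exposed, the false-positive rate is 63%.

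**Precision after restriction to unexposed controls.** Half-width of the 95% CI = t(0.975, 28 + m) × 3.33 × √(1/30 + 1/m), with m unexposed controls against 30 epidural patients:

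| m | Half-width | Power for 2.665 |
|---|---|---|
| 30 | 1.72 | 0.862 |
| 23 | 1.85 | 0.809 |
| 20 | 1.93 | 0.775 |
| 15 | 2.12 | 0.696 |

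**Does restriction reduce total error?** Starting from 30 controls:
- All controls: RMSE = √(3.33² × 2/30 + (f × effect)²).
- Unexposed only: RMSE = 3.33 × √(1/30 + 1/(30(1 − f))).
- These are equal when effect = 3.33 / √(30 f(1 − f)): 1.40 units at f = 0.25 and 1.22 at f = 0.50.

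At a 1-unit effect, restriction has the larger RMSE: 0.929 against 0.895 at f = 0.25, and 1.053 against 0.995 at f = 0.50. At 2 units and f = 0.50 it has the smaller: 1.053 against 1.319. The size of the effect is unknown, so these figures support showing both analyses. They do not support making the restricted one primary.

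**The case against.** **IMOX practice may already match.** The same Zealand center initiated this study, and withholding dexamethasone at Hvidovre may have been meant to align the two cohorts. This stands as a possibility. A reader might infer that IMOX patients did receive dexamethasone and that the epidural contrasts are therefore biased. The documents do not support that: only the Hvidovre procedure is appended, and nothing describes Zealand practice either way.

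**Medication data are already planned.** The medication item, together with the promised table of clinical characteristics by anesthesia type, suggests that some IMOX data beyond outcomes will be obtained. Two of the three groups come only from IMOX, so that table does need such data. This narrows the gap. It does not close it, because dexamethasone is not named, the medication item is not extended to IMOX, and neither place says what to do if exposure differs.

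**Individual exposure data may be unnecessary.** It is tempting to say that only patient-level retrieval can rule this bias out. That goes too far: a documented statement that IMOX did not use perioperative dexamethasone would largely settle the matter.

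**Hospital confounding is larger.** Epidural is wholly tied to hospital, and the study calls itself exploratory. Both are true, and removing one co-medication does not make either contrast causal. Dexamethasone is nevertheless one component that the protocol itself identifies, and it can be partly separated if some controls were unexposed.

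**Conclusion.** The point holds as a gap in the plan. A modulator named in the protocol is controlled in the epidural group and is neither described nor handled in the controls. The gap can be read directly from the text. Whether it causes bias, in which direction and how much, cannot be derived from the documents.

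The error rates above rest on an assumed effect, exposure share and control split, and are illustrations only. At a 1-unit effect with 25% or fewer exposed, the false-positive rate stays near nominal. With wider exposure or a larger effect it does not. If no IMOX patient was exposed, there is no dexamethasone bias. Hospital confounding of both epidural contrasts remains in every case.

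This should be fixed because the remedy is cheap. Confidence is medium, since the exposure is undocumented.

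**What to change.** 1. State the IMOX/Zealand practice on perioperative dexamethasone.
2. Unless it is documented as not used, add exposure (yes/no, dose) to the electronic data retrieved from IMOX and tabulate it by anesthetic group with the clinical characteristics.
3. If any controls were exposed, report both epidural contrasts in all technique-eligible controls and, as a pre-specified sensitivity analysis, in unexposed controls only, each with its confidence interval.
4. State that an epidural contrast is confounded by dexamethasone if it has no unexposed controls, and possibly confounded if exposure cannot be recovered. State hospital confounding in every case.

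**Cost.** One extra variable, a table row and a few sentences. The restricted analysis is less precise: for example, a 95% CI half-width of 2.12 with 15 unexposed controls against 1.72 with 30. No treatment changes.

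**Separate wording point, not part of the weight given here.** Risks, harms and inconveniences says the study influences no treatment, while the Intervention section withholds a drug listed in the hospital's own procedure. The two passages must be reconciled.

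### Eligibility is defined for the Hvidovre epidural group only and no case-mix adjustment is planned, so the two epidural contrasts can mix case mix with epidural use

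*Combined protocol and SAP*

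**What the plan says.** Under Eligibility criteria, the Hvidovre group is limited to "Patients diagnosed with colorectal cancer (UICC stadium I-III) and scheduled for laparoscopic hemicolectomy", age over 18 and ASA I-III. Six exclusions follow: immune defects, "Patients undergoing neoadjuvant chemo or radiotherapy", previous cancer, immunomodulatory treatment, daily steroids and recent major surgery.

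Under Control group, IMOX is described in one line on case mix: "It is a prospective explorative study cohort that consists of 60 patients undergoing laparoscopic colorectal cancer surgery". The only selection rule stated for these patients concerns technique: they are split into total intravenous anesthesia (TIVA) or sevoflurane, and "Patients anaesthetized with other techniques including epidural or other regional blocks will be excluded from the analysis".

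The Sample size section says of the Hvidovre participants: "They will be compared to the patients included in the IMOX-study at Zealand University Hospital". No restriction is attached. The planning figures are "based on a pilot study of 45 patients undergoing laparoscopic hemicolectomy".

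The Data analysis section combines the two populations. "Baseline and clinical characteristics for patients, stratified for anesthesia type will be presented", and "differences between the groups will be assessed using parametric or non-parametric statistics, respectively". No covariate, matching, weighting or restriction is named.

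**The concern.** The primary outcome is an immune-cell ratio, and the plan protects it on the Hvidovre side by excluding conditions that could disturb it. The same protection is not stated for the controls. The operation is also described more broadly for IMOX (colorectal surgery) than for Hvidovre (hemicolectomy). IMOX may therefore include rectal resections, neoadjuvant treatment or other conditions that Hvidovre excludes.

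If procedure, stage, ASA class or the excluded conditions differ between hospitals, the difference in the change in neutrophil to lymphocyte ratio (NLR) is partly a difference between kinds of patient. That could create an apparent epidural effect or hide a real one. The planned baseline table would show an imbalance in the variables it contains, but would not correct it.

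**Working it through.** **1. The documents side by side**

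| Item | Hvidovre (epidural) | IMOX (controls) |
|---|---|---|
| Operation | Laparoscopic hemicolectomy | Laparoscopic colorectal cancer surgery |
| Stage, ASA, age | UICC I-III, ASA I-III, over 18 | Not stated |
| Exclusions 1-6 | Stated | Not stated |
| Selection by technique | TIVA plus epidural | TIVA or sevoflurane; epidural excluded |
| Withdrawal rules, dexamethasone omission | Stated | Not stated |

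Three groups give three pairwise contrasts. The two that involve epidural cross hospitals; sevoflurane versus TIVA does not.

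**2. The plan's sample size**

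Inputs from the Sample size section: rise 5.33, SD 3.33, a 50% smaller rise, alpha 0.05 (two-sided, from the statistical analysis plan), power 0.8.

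- Target difference = 0.5 × 5.33 = 2.665.
- n per group = 2 × [3.33 × (1.960 + 0.842) / 2.665]² = 24.5, rounded up to 25.

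The stated 25 reproduces as a per-group figure for two groups. The calculation has no term for a case-mix difference, and its inputs come from hemicolectomy patients.

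**3. What a mismatch could do (illustration; every share and difference is assumed)**

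Let a share s of controls fall outside the Hvidovre criteria, with a mean NLR rise that differs by d. Take 30 versus 30 patients and a two-sided t-test with 58 df.

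- Bias = s × d.
- Control SD = √[3.33² + s(1 − s)d²].
- SE = √[(3.33² + control SD²) / 30].

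| s | d | Bias | Share of 2.665 | Control SD | False-positive rate | Power if the bias masks the target |
|---|---|---|---|---|---|---|
| 0 | 0 | 0 | 0% | 3.330 | 5.0% | 0.86 |
| 0.10 | 1 | 0.1 | 4% | 3.343 | 5.1% | 0.83 |
| 0.30 | 2 | 0.6 | 23% | 3.454 | 10.3% | 0.64 |
| 0.40 | 3 | 1.2 | 45% | 3.640 | 25.8% | 0.36 |

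The last row assumes a difference larger than the whole target. The table shows how the mechanism scales; it does not estimate this study.

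**4. What restriction costs**

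Power for 30 epidural patients against n controls, with difference 2.665, SE = 3.33 × √(1/30 + 1/n) and 28 + n df:

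| Controls n | 30 | 27 | 24 | 23 | 22 | 21 | 18 | 15 |
|---|---|---|---|---|---|---|---|---|
| Power | 0.86 | 0.84 | 0.82 | 0.81 | 0.80 (0.798) | 0.79 | 0.75 | 0.70 |

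Thirty per technique is an even split of all 60. The actual split is not given, and patients given other techniques are removed first; if those were 10%, an even split would start at 27.

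**5. Why restriction should not depend on a minimum count**

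Power of 0.8 needs 23 controls. From 30 per technique, 30% outside the criteria leaves 30 × 0.7 = 21, and 40% leaves 30 × 0.6 = 18. A power-based threshold would abandon restriction in the very cases where the illustrated bias is largest.

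**The case against.** **IMOX may have the same criteria.** It may. It is a separate study summarised here in a few sentences, so the mismatch is possible and not shown. A reader might infer that IMOX does contain rectal or neoadjuvant cases, or that the epidural contrasts are biased by a known amount. The documents support neither: the broader wording does not rule such cases out, but nothing confirms them. If the criteria match, saying so settles most of this point.

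**The variables are already listed.** Partly right. The Data collection and management section names age, comorbidities, stage, surgical procedure, medication and anesthesia type, plus ASA, immune defects and steroid use at screening. The baseline table must also include IMOX patients, since the sevoflurane and TIVA-only groups exist only there. But the list is written for Hvidovre participants and is not extended to the IMOX transfer, for which the plan mentions the main outcomes.

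**IMOX may not have recorded every exclusion.** This stands. The common criteria can be applied only as far as they were recorded.

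**Hospital is confounded with epidural use anyway.** This also stands, and it is the larger limitation. Every epidural patient is at Hvidovre and IMOX epidural patients are excluded, so no restriction or model separates the two. It is a reason to word the conclusions as associations, not to leave measurable case-mix differences uncorrected.

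**The study is exploratory.** The plan says so, but it also sets a significance level, powers a 50% difference and aims to evaluate effects. Exploratory status does not make the groups comparable.

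**Conclusion.** The concern holds as an omission in both design and analysis. Eligibility is stated on one side of a non-randomised, two-hospital comparison, and the comparison itself is unadjusted. Followed as written, the plan leaves any measured case-mix difference in the two epidural contrasts uncorrected. The effect on those contrasts is of unknown size and direction and may be zero; the illustrated false-positive rates of 5.0% to 25.8% rest on inputs that no document supports and should not set the weight of the point. The planned sample size of 25 is arithmetically sound. A reader might extend the criticism to all three comparisons, but sevoflurane versus TIVA is drawn from one cohort and this asymmetry does not touch it. The change should be made before the IMOX data are transferred.

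**What to change.** 1. **Criteria and variables.** State IMOX's eligibility criteria. Extend the variable list in Data collection and management to the IMOX transfer: procedure, stage, ASA, age, comorbidities, medication including steroids, and immune defects. Add neoadjuvant therapy, previous cancer, immunomodulators and recent major surgery where IMOX recorded them.
2. **Primary set.** For both epidural contrasts, use the IMOX patients who meet inclusion criteria 1-3 and none of exclusions 1-6, as far as recorded and whatever number remains. Report how many remain per technique and which criteria could not be checked.
3. **Primary analysis.** Replace the unadjusted test with a prespecified linear model of NLR change on anesthesia group, adjusted for a short fixed list (procedure, stage, ASA, age), in that restricted set. Report the full IMOX set as a sensitivity analysis, adding the recorded exclusion conditions as covariates.
4. **Limits.** State that hospital is fully aliased with epidural use. State also that the withdrawal rules and the dexamethasone omission, described only for Hvidovre, remain as differences. The epidural contrasts should be reported as associations.

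**Cost.** Additional named variables in the transfer, as far as IMOX holds them, and some wording in the analysis plan. Precision lost by restriction cannot be bought back within IMOX, a fixed cohort of 60: power falls from about 0.86 with 30 controls to 0.82 with 24, 0.79 with 21, 0.75 with 18 and 0.70 with 15. These figures are for the unadjusted comparison. Adjustment costs a little more if the covariates are related to group and explain none of the outcome: at 30 versus 30 with six covariate df, power is 0.86, 0.82 or 0.78 if they explain 0, 10 or 20% of group membership. Covariates that predict NLR change would win some of that back. The achieved power should be restated once the counts per technique are known.
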